6.4 Trial Flow Chart for Combination Therapy (Part B)

Trial Period:	Screening Phase		Treatment Period								End of Treatment				
	Treatment Cycle/Title:	Pre-screening	Screening	Wk 1	Wk 2	Wk 3	Wk 4	Wk 5	Wk 6	Wk 7	Wk 8	Discon	Follow-up Phone Call	Follow up	Follow Up
Scheduling Window (Days):			-28 to -1	± 3 ¹		± 3		± 3		± 3		At time of Discon	30 days post	90 days post	Every 8 weeks post
Administrative Procedures															
Pre-screening Consent (H&N subjects only)	X														
HPV+ Test (H&N subjects only)	X														
Informed Consent		X													
Inclusion/Exclusion Criteria		X													
Subject Identification Card		X													
Demographics and Medical History		X													
Prior and Concomitant Medication Review		X	X		X		X		X						
MEDI4736 Administration (Q2wk)		X		X		X		X		X					
ADX11-001 Administration (Q4wk) ²			X				X								
Clinical Procedures/Assessments															
Review Adverse Events				X		X		X		X		X	X	X	
Physical Examination ³		X	X		X		X		X		X				
Vital Signs and Weight ⁴		X	X		X		X		X		X				
ECOG Performance Status		X	X		X		X		X		X				
Tumor Imaging ⁵		X	X								X			X	
Laboratory Assessments⁶															
Pregnancy Test – Urine or Serum β-HCG		X	X		X		X		X						
PT/INR and aPTT		X	X		X		X		X		X				
CBC with Differential		X	X		X		X		X		X				
Comprehensive Serum Chemistry Panel		X	X		X		X		X		X				
Urinalysis		X	X		X		X		X		X				
T3, T4 and TSH		X	X		X		X		X		X				
Tissue/Blood Collection															

Trial Period:	Screening Phase		Treatment Period								End of Treatment				
	Treatment Cycle/Title:	Pre-screening	Screening	Wk1	Wk 2	Wk 3	Wk 4	Wk 5	Wk 6	Wk 7	Wk 8	Discon	Follow-up Phone Call	Follow up	Follow Up
Scheduling Window (Days):		-28 to -1	$\pm 3^1$		± 3		± 3		± 3		± 3	At time of Discon	30 days post	90 days post	Every 8 weeks post
PK Assessment ¹⁰				X		X		X		X		X		X	
Immunogenicity (ADA) Assessment (serum) ¹¹			X				X		X		X		X		

1 - The \pm 3 day window does not apply to Cycle 1, Week 1. This window is only applicable in all subsequent cycles.

2 - Subjects will receive prophylactic NSAIDS and antiemetics [REDACTED] before each ADXS11-001 infusion. Subjects will also receive a course of oral antibiotics to be started 3 days after each ADXS11-001 infusion

3 - ECG and O₂ saturation by pulse oximetry at baseline screening only

4 - Vital signs are to be monitored [REDACTED] following each ADXS11-001 infusion.

5 - Tumor Assessments will be done in screening and Week 1 (\pm 1 week), starting at Cycle 2. Evaluations will continue every 8 weeks (\pm 1 week) during treatment and for subjects in follow up who discontinue treatment for reasons other than disease progression; duration of follow up will be up to 3 years.

6 - Screening lab that are done within 5 days of initiating treatment can be used for C1D1 laboratory tests.

7 - [REDACTED]

8 - [REDACTED]

9 - [REDACTED]

10 - PK Assessment: Serum will be collected at Cycle 1 Day 1 (pre-dose and end of infusion), at Weeks 3 and 5 (pre-dose only) and at Week 7 (pre-dose and end of infusion). For all subsequent cycles, serum will be collected at Week 7 (pre-dose only) with the exception of Cycle 3 where serum will be collected at Week 7 (pre-dose and end of infusion). Serum will also be collected at end of treatment and at the 90-day post treatment follow up visit.

11 - Immunogenicity (ADA) Assessment: Serum will be collected at Cycle 1 Day 1 (pre-dose only), at Weeks 5 and 7 (pre-dose only). For all subsequent cycles, serum will be collected at Week 7 (pre-dose only). Serum will also be collected at end of treatment and at the 90-day post treatment follow up visit.

12 - [REDACTED]

13 - [REDACTED]

6.5 Retreatment Flow Chart

	Rebaseline	Retreatment Period (up to 1 Year)						Every 8 weeks After 1 year of retreatment
		Week 1	Week 3	Week 5	Week 7	Week 8		
Informed re-consent	X							
Inclusion/Exclusion criteria	X	X						
Medical history (update)	X							
Prior/Concomitant medication	X	X	X	X	X			
MEDI4736 Administration		X	X	X	X			
Prophylactic Medications ¹ (ADXS11-001 only)		X		X				
ADXS11-001 Administration			X		X			
PO antibiotics and instructions ² (ADXS11-001 only)			X		X			
AE/SAE Assessment ³			X	X	X	X		
Physical examination ⁴	X	X	X	X	X			
Vital signs ⁵	X	X	X	X	X			
ECOG performance status	X	X	X	X	X			
CBC with Differential ⁶	X	X	X	X	X			
Chemistry Panel ^{6,7}	X	X	X	X	X			
PT/INR and aPTT ⁷	X	X	X	X	X			
Urinalysis ⁷	X	X	X	X	X			
T3, T4 and TSH ⁷	X	X	X	X	X			
Pregnancy test	X	X	X	X	X			
Tumor Imaging ⁸		X						X

- 1 - Subjects will receive prophylactic NSAIDS and antiemetics [REDACTED] before each ADXS11-001 infusion
- 2 - Subjects will receive a course of oral antibiotics to be started 3 days after each ADXS11-001 infusion
- 3 - Safety Follow up will be conducted via telephone. Safety Follow up at 30 days (\pm 1 week) for AEs and at 90 days (\pm 1 week) for SAEs.
- 4 - ECG and O₂ saturation by pulse oximetry at re-baseline only
- 5 - Vital signs are to be monitored [REDACTED] following each ADXS11-001 infusion.
- 6 - Subjects must meet hepatic and renal function eligibility criteria prior to dosing
- 7 - Refer to [Table 9](#) for a full listing of laboratory tests
- 8 - Tumor Assessments will be on Week 1 (\pm 1 week), starting at [Cycle 2](#). Evaluations will continue every 8 weeks (\pm 1 week) during treatment and continue for subjects in follow up who discontinue retreatment for reasons other than disease progression; duration of follow up will be up to 3 years.

7.0 TRIAL PROCEDURES

7.1 Trial Procedures

The Trial Flow Chart - Section [6.0](#) summarizes the trial procedures to be performed at each visit. Individual trial procedure details are described in detail below. It may be necessary to

perform these procedures at unscheduled time points if deemed clinically necessary by the investigator.

Additional evaluations/testing deemed necessary by the Sponsor for reasons related to subject safety will be incorporated into a protocol amendment but can be implemented prior to IRB approval for safety concerns. In these cases, such evaluations/testing will be performed in accordance with those regulations.

7.1.1 Administrative Procedures

7.1.1.1 Informed Consent

The Investigator must obtain documented consent from each potential subject prior to participating in a clinical trial.

Consent must be documented by the subject's dated signature on a consent form along with the dated signature of the person conducting the consent discussion.

A copy of the signed and dated consent form should be given to the subject before participation in the trial.

The pre-screen consents, initial informed consent form, any subsequent revised initial informed consent form, any re-consent forms and any written information provided to the subject must receive the IRB's approval/favorable opinion in advance of use. The subject should be informed in a timely manner if new information becomes available that may be relevant to the subject's willingness to continue participation in the trial. The communication of this information will be provided and documented via a revised consent form or addendum to the original consent form that captures the subject's dated signature.

Specifics about a trial and the trial population will be added to the consent form template at the protocol level.

The informed consent will adhere to IRB requirements, applicable laws and regulations and Sponsor requirements.

7.1.1.2 Inclusion/Exclusion Criteria

All inclusion and exclusion criteria will be reviewed by the investigator or qualified designee to ensure that the subject qualifies for the trial.

7.1.1.3 Subject Identification Card

All subjects will be given a Subject Identification Card identifying them as participants in a research trial. The card will contain trial site contact information (including direct telephone numbers) to be utilized in the event of an emergency. The investigator or qualified designee will provide the subject with a Subject Identification Card after the subject provides written informed consent.

7.1.1.4 Medical History

A medical history will be obtained by the investigator or qualified designee. Medical history will include all active conditions, and any condition diagnosed within the prior 10 years that are considered to be clinically significant by the Investigator. Details regarding the disease for which the subject has enrolled in this study will be recorded separately and not listed as medical history.

7.1.1.5 Prior and Concomitant Medications Review

7.1.1.5.1 Prior Medications

The investigator or qualified designee will review prior medication use, including any protocol-specified washout requirement, and record prior medication taken by the subject within 28 days before starting the trial. Treatment for the disease for which the subject has enrolled in this study will be recorded separately and not listed as a prior medication.

7.1.1.5.2 Concomitant Medications/Therapies

The investigator or qualified designee will record medication/therapy, if any, taken by the subject during the trial. All medications/therapies related to reportable SAEs and ECIs should be recorded as defined in Section [7.2](#).

7.1.1.6 Disease Details and Treatments

7.1.1.6.1 Disease Details

The investigator or qualified designee will obtain prior and current details regarding disease status.

7.1.1.6.2 Prior Treatment Details

The investigator or qualified designee will review all prior cancer treatments including systemic treatments, radiation and surgeries.

7.1.2 Clinical Procedures/Assessments

7.1.2.1 Adverse Event (AE) Monitoring

The investigator or qualified designee will assess each subject to evaluate for potential new or worsening AEs as specified in the Trial Flow Chart and more frequently if clinically indicated. Adverse experiences will be graded and recorded throughout the study and during the follow-up period according to NCI CTCAE Version 4.03 (see Section 13.2). Toxicities will be characterized in terms regarding seriousness, causality, toxicity grading, and action taken with regard to trial treatment.

All AEs of unknown etiology associated with the study drug(s) exposure should be evaluated to determine if it is possibly an event of clinical interest (ECI) of a potentially immunologic etiology (irAE). See Section 5.2.1.1 regarding the identification, evaluation and management of AEs of a potential immunological etiology.

Please refer to Section 7.2 for detailed information regarding the assessment and recording of AEs.

7.1.2.2 Physical Examination

The investigator or qualified designee will perform a physical examination during the screening period (including baseline screening ECG and O₂ saturation by pulse oximetry), prior to the administration of each dose of trial treatment and at treatment discontinuation as

specified in the Trial Flow Chart (Section 6.0). Clinically significant abnormal findings should be recorded as medical history.

7.1.2.3 Vital Signs

The investigator or qualified designee will take vital signs at screening, prior to the administration of each dose of trial treatment, [REDACTED] following each ADXS11-001 infusion and at treatment discontinuation as specified in the Trial Flow Chart (Section 6.0). Vital signs should include temperature, pulse, respiratory rate, and blood pressure. Height will be measured at screening only and weight will be measured pre-dose at each visit.

7.1.2.4 Eastern Cooperative Oncology Group (ECOG) Performance Scale

The investigator or qualified designee will assess ECOG status (see Section 13.1 ECOG Performance Status) at screening, prior to the administration of each dose of trial treatment and discontinuation of trial treatment as specified in the Trial Flow Chart- Section 6.1.

7.1.2.5 Tumor Imaging and Assessment of Disease

Computed tomography (CT) and magnetic resonance imaging (MRI) will be considered the best currently available and reproducible methods to measure target lesions selected for response assessment. Conventional CT should be performed with contiguous cuts of 10 mm or less. Spiral CT scan should be performed using a 5 mm contiguous reconstruction algorithm (as a general rule, lesion diameter should be no less than double the slice thickness). Lesions on chest x-rays will be acceptable as measurable lesions when they are clearly defined and surrounded by aerated lung; however, CT is preferable. Ultrasound is not an acceptable method to measure disease.

Assessment of disease will be done using both RECIST 1.1 criteria and irRECIST criteria.

7.1.2.6 Measurable and Non-measurable Lesions and Disease

Measurable lesions will be those that can be accurately measured in at least one dimension with the longest diameter ≥ 10 mm (for spiral CT scan or MRI scan, ≥ 5 mm). Measurable disease will be present if the subject has 1 or more measurable lesions.

Non-measurable lesions/disease will be all other lesions (or sites of disease), including small lesions (those with all measurements <10 mm or <5 mm with spiral CT/MRI), or any of the following: bone lesions, leptomeningeal disease, ascites, pleural or pericardial effusion, lymphangitis, cutis/pulmonis, abdominal masses that are not confirmed and followed by imaging techniques, cystic lesions, and lesions occurring within a previously irradiated area unless they are documented as new lesions since the completion of radiation therapy.

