7.1.2.7 Target/Non-Target Lesions

All measurable lesions, up to a maximum of 2 per organ and 5 in total, should be identified as target lesions to be measured and recorded at baseline. The target lesions should be representative of all involved organs. Target lesions will be selected based on their size (the lesion with the longest diameter) and suitability for accurate repeated measurements. At baseline, a sum of the longest diameters for all target lesions will be calculated and recorded as the baseline tumor burden. The baseline sum will be used as the reference point to determine the objective tumor response of the target lesions.

Measurable lesions other than the target lesions and all sites of non-measurable disease will be identified as non-target lesions and will be recorded at baseline. Non-target lesions will be evaluated at the same time points as target lesions.

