7.1.2.8 Response in Measureable Lesions (RECIST 1.1)

At baseline, the sum of the longest diameters (SumD) of all target lesions (up to 2 lesions per organ, up to total 5 lesions) is measured. At each subsequent tumor assessment, the SumD of the target lesions and of new, measurable lesions (≥ 10 mm; up to 2 new lesions per organ,

total 5 new lesions) are added together to provide the total measurable tumor burden (TMTB):

$$\text{TMTB} = \text{SumD target lesions} + \text{SumD new, measurable lesions}$$

Percentage changes in TMTB per assessment time point describe the size and growth kinetics of both old and new measurable lesions as they appear. At each tumor assessment, the response in target and new measurable lesions is defined based on the change in TMTB.

- Complete Response (CR): Disappearance of all target lesions. Any pathological lymph nodes (whether target or non-target) must have reduction in short axis to <10 mm.
- Partial Response (PR): At least a 30% decrease in the sum of diameters of target lesions, taking as reference the baseline sum diameters.
- Progressive Disease (PD): At least a 20% increase in the sum of diameters of target lesions, taking as reference the smallest sum on study (this includes the baseline sum if that is the smallest on study). In addition to the relative increase of 20%, the sum must also demonstrate an absolute increase of at least 5 mm. (Note: the appearance of one or more new lesions is also considered progression).
- Stable Disease (SD): Neither sufficient shrinkage to qualify for PR nor sufficient increase to qualify for PD, taking as reference the smallest sum diameters while on study.

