7.1.2.12 Overall Response

Overall response will be determined based on RECIST 1.1 criteria and by irRECIST criteria (Table 1). Overall response according to irRECIST is derived from the responses in measurable lesions (based on TMTB) and the presence of any non-measurable lesions.

Table 6 Tumor Response Evaluation: Comparison of RECIST 1.1 and irRECIST

Criteria	RECIST1.1	irRECIST
New measurable lesions (≥ 10 mm)	Always represents PD	Incorporated into tumor burden
New non-measurable lesions (< 10 mm)	Always represents PD	Does not define progression but precludes irCR
Non-Target lesions	Changes contribute to defining BOR of CR, PR, SD, and PD	Contribute to defining irCR (complete disappearance required)
CR	Disappearance of all lesions	Disappearance of all lesions
PR	$\geq 30\%$ decrease in the sum of the longest diameter of all target lesions compared with baseline, in absence of new lesions or unequivocal progression of non-target lesions	$\geq 30\%$ decrease in tumor burden compared with baseline
SD	Neither sufficient shrinkage to qualify for PR nor sufficient increase to qualify for PD, taking as reference the smallest sum diameters while on study	Neither a 30% decrease in tumor burden compared with baseline nor a 20% increase compared with nadir can be established
PD	At least 20% increase in sum of diameters of target lesions, taking as reference the smallest sum on study. In addition to the relative increase of 20%, the sum must also demonstrate an absolute increase of at least 5mm. The appearance of one or more new lesions is also considered progression.	At least 20% increase in tumor burden compared with nadir (at any single time point) ^a

irRECIST = immune-related Response Evaluation Criteria in Solid Tumors; BOR = best overall response; CR = complete response; irCR = immune-related complete response; PD = progressive disease; PR = partial response; SD = stable disease;

^a Patients with an initial finding of progressive disease (irPD) before or at the 9-week imaging assessment, but without rapid clinical deterioration, require confirmation of irPD with a second, consecutive scan obtained ≥ 4 weeks from the initiation documentation. Patients will continue to receive study treatment until irPD is confirmed at this later time point. Best overall response (BOR) will therefore include responses occurring at any time before disease progression and after early progression (i.e., within the first 8 weeks of the study).

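### Section 7.1.2.6 counts 5 mm lesions as measurable on spiral CT or MRI, while the plan's own slice rule and new-lesion cut-off give 10 mm; where such a lesion is the only target, a 1.5 to 2 mm reading change is enough for a PR

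*Combined protocol and SAP*

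**What the plan says.** Section 7.1.2.6 calls a lesion measurable at "longest diameter ≥ 10 mm (for spiral CT scan or MRI scan, ≥ 5 mm", and treats as non-measurable all other lesions, "including small lesions (those with all measurements <10 mm or <5 mm with spiral CT/MRI".

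Section 7.1.2.5 gives the scan settings: "Spiral CT scan should be performed using a 5 mm contiguous reconstruction algorithm", with the general rule that "lesion diameter should be no less than double the slice thickness". For conventional CT it says "Conventional CT should be performed with contiguous cuts of 10 mm or less". It gives no slice thickness for MRI.

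For new lesions the cut-off is 10 mm. Sections 7.1.2.8 and 7.1.2.9 add new lesions to the tumor burden from 10 mm, Section 7.1.2.11 says non-measurable lesions start to count once they reach 10 mm, and Table 6 has the row "New non-measurable lesions (< 10 mm").

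On lymph nodes, Section 7.1.2.7 says "a sum of the longest diameters for all target lesions will be calculated and recorded as the baseline tumor burden", with no exception for nodes, and neither it nor Section 7.1.2.6 gives a nodal minimum. Short axis appears only in the CR rules (Section 7.1.2.8: "Any pathological lymph nodes (whether target or non-target) must have reduction in short axis to <10 mm"; Sections 7.1.2.9 and 7.1.2.10 are similar) and in the irRECIST rule that a new node must be at least 15 mm in shortest diameter (Section 7.1.2.9).

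**The concern.** The plan gives two answers to what is large enough to measure. On spiral CT the lower answer equals one reconstruction interval and is half of what the plan's own general rule asks for. It also splits baseline from new disease: on spiral CT or MRI a 7 mm lesion is measurable if present at baseline and non-measurable if it appears later.

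This matters for response. PR is a 30% fall in the sum with no absolute minimum, under both RECIST 1.1 and irRECIST, so for a very small sum the threshold lies within plausible reading error. Tumor response is a Part B primary objective (Section 3.4) and the arms are small. The trial is open-label, and the only response assessor named is the investigator (Section 2.1, for Part A). Section 13.3 mentions central review only for an exploratory volumetric analysis. Section 7.1.2.12.1 refers to any requirement for confirmation of response, but none is specified.

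**Working it through.** **1. The slice rule.** Inputs from Section 7.1.2.5: 5 mm spiral reconstruction, 10 mm maximum conventional cut, factor of 2.
- Spiral CT: 2 × 5 = 10 mm, against 5 mm in Section 7.1.2.6. The plan's 5 mm figure is not reproduced; it would need slices of 5 / 2 = 2.5 mm or thinner, which the plan does not specify.
- Conventional CT at the thickest permitted cut: 2 × 10 = 20 mm, against 10 mm in Section 7.1.2.6. The 10 mm limit agrees with the rule only for cuts of 5 mm or less.

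**2. Change needed for PR.** Required fall = 0.30 × baseline sum.
- One 5 mm target: 0.30 × 5 = 1.5 mm (5 to 3.5 mm).
- One 6 mm target read as 4 mm: (6 − 4) / 6 = 33%, a PR from 2 mm.
- One 10 mm target: 0.30 × 10 = 3.0 mm.

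**3. Chance of a false PR at one assessment.** The documents give no reading error, so the SD per reading, s, is an assumption: 1.0 mm, range 0.5 to 1.5 mm. Take a lesion of true size d that does not change, with independent normal errors at baseline and follow-up. PR is declared if follow-up ≤ 0.7 × baseline. The quantity follow-up − 0.7 × baseline has mean 0.3d and variance s²(1 + 0.49), so

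P(false PR) = Φ(−0.3d / (s√1.49)).

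For d = 5 and s = 1.0: −1.5 / 1.221 = −1.23, giving 11.0%.

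| Assumed SD | One 5 mm target | One 10 mm target |
|---|---|---|
| 0.5 mm | 0.7% | 0.0% |
| 1.0 mm | 11.0% | 0.7% |
| 1.5 mm | 20.6% | 5.1% |

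Simulation agrees with these figures.

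**4. Dilution with more targets.** With independent errors, the SD of a sum of k lesions is s√k while the threshold grows with k. At s = 1.0 mm and 5 mm lesions, the false-PR rate is 11.0% for one target, 4.1% for two and 0.3% for five.

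**5. Effect on the response rate.** Part B has 48 subjects allocated 1:1:2 (Section 1.0): 12, 12 and 24. One subject is 1/12 = 8.3 points or 1/24 = 4.2 points, if all randomized subjects are in the denominator.

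**6. Nodes, by comparison of text.** A node 12 mm long and 8 mm in short axis passes the longest-diameter test of Section 7.1.2.6. Its short axis is already below the 10 mm that the CR rule asks for, and below the 15 mm that a new node needs under irRECIST. No text says how such a node is handled at baseline.

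**The case against.** The strongest defense is that the plan has safeguards. The double-slice rule is only a general rule. Section 7.1.2.6 requires lesions that can be accurately measured, and Section 7.1.2.7 selects targets by size and repeatability, up to five. A 5 mm lesion should therefore rarely be the only target. That stands as a limit on frequency. It does not remove the conflict: one measurable lesion suffices, and Section 7.1.2.7 also wants all measurable lesions up to its caps taken as targets and all involved organs represented.

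Several stronger readings are tempting but not supported:
- *False irPD also moves the response rate.* A 5 mm nadir read as 6 mm is +20%, but a change from SD to irPD moves a subject between two non-responder categories. Section 7.1.2.9 asks for confirmation after 4 weeks in the absence of clinical deterioration, and the Table 6 footnote requires a second scan for irPD at or before the 9-week assessment.
- *irPD needs a 5 mm absolute floor.* Section 7.1.2.9 and Table 6 agree that there is none. Adding one would be a preference, not a correction.
- *PFS by RECIST 1.1 is distorted.* RECIST PD on target size needs a 5 mm absolute increase. For one stable 5 mm lesion, false PD is about 0.02% at an SD of 1.0 mm (0% to 0.9% over the range).
- *The 12 × 8 mm node is certainly a target, or breaches the size rules.* Its 12 mm length meets both the double-slice rule at 5 mm and the 10 mm cut-off, and Section 7.1.2.10 calls a short axis under 10 mm non-pathological. The nodal problem is an omission.
- *Section 7.1.2.6 sets eligibility.* Inclusion criterion 5 cites RECIST 1.1 and does not point to this section. Which governs is unstated.
- *MRI breaches the slice rule too.* No MRI slice thickness is given, so this cannot be shown. The MRI allowance still conflicts with the 10 mm new-lesion cut-off.

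The mismatch between baseline and new lesions also matters mainly under irRECIST, since Table 6 makes any new lesion PD under RECIST 1.1.

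**Conclusion.** The concern holds in limited form. The 5 mm allowance contradicts the general slice rule for spiral CT and the 10 mm cut-off used for new lesions. That conclusion rests on the text alone and needs no assumption.

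The consequence is a possible false PR in subjects with few or no larger lesions. The 1.5 to 2 mm change and the 8.3 or 4.2 points per misclassified subject are plain arithmetic. The frequency, about 11% per assessment for a single stable 5 mm target, is conditional on an assumed SD of 1.0 mm and on independent normal errors. It is not an estimate of the trial-wide false response rate, because the documents do not say how many subjects would have only such lesions.

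The missing baseline nodal rule is a separate, smaller gap.

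**What to change.** 1. In Section 7.1.2.6, remove the 5 mm allowance for spiral CT and MRI from both the measurable and the non-measurable definitions. State one minimum for baseline and new lesions: longest diameter at least 10 mm and at least double the slice thickness. The second condition also covers thick conventional cuts.
2. State a baseline nodal rule, applying the 15 mm short-axis limit that Section 7.1.2.9 already uses for new nodes. If nodes are then summed by short axis, amend Sections 7.1.2.7, 7.1.2.8 and 7.1.2.9 together, since all three now sum longest diameters and changing one alone would create a new contradiction.
3. State that inclusion criterion 5 uses this definition, so that eligibility and response rest on the same lesions.

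The cost is a wording amendment. The downside is that a few subjects whose only lesions are 5 to 9 mm, or whose only disease is in small nodes, would fail screening.
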